8.8.3 Classification of an adverse event

8.8.3.1 Severity of adverse events

The investigator is to classify the severity (intensity) of an AE according to the following definitions:

- Mild – The patient was aware of the signs and symptoms, but the signs and symptoms were easily tolerated and does not interfere with daily activity.
- Moderate – The signs and symptoms were sufficient to restrict, but did not prevent, usual daily activity for the patient. The patient is still able to function.
- Severe – The patient was unable to perform usual daily activities.

The maximum severity recorded during the course of an AE (mild, moderate, or severe) will be considered the final severity.

8.8.3.2 Relationship of adverse events to trial treatment

The investigator is responsible for assessing the relationship of an AE to the IMP treatment using good clinical judgment and the following definitions:

- Not related – The AE is clearly explained by another cause not related to the IMP administration; the temporal relationship of the AE to IMP administration makes a causal relationship clearly improbable or concomitant medication, therapeutic interventions, or underlying condition provide a sufficient explanation for the observed AE.

- Unlikely related – The AE is most likely related to aetiology other than the IMP administration; the temporal relationship of the AE to IMP administration makes a causal relationship unlikely, and other concomitant medication, therapeutic interventions or underlying disease provide plausible explanations for the observed AE.
- Possibly related – The AE and administration of IMP are temporally related, but the AE can be explained equally well by causes other than the IMP administration. A causal relationship is conceivable and cannot be dismissed.
- Probably related – The AE and use of IMP are temporally related, and the AE is more likely explained by IMP administration than by other causes. Good reason and sufficient documentation to assume a causal relationship.

The last relationship recorded during the course of an AE will be considered the final relationship as the investigator is assumed to have had the most information to perform the relationship assessment at that time.

8.8.3.3 Outcome of adverse events

The outcome of an AE will be classified as:

- Recovered/resolved
- Recovered/resolved with sequelae (note: in case of sequelae, the sequelae must be reported as a comment in the eCRF)
- Recovering/resolving
- Not recovered/not resolved
- Fatal
- Unknown

8.8.4 Time period and frequency for event assessment and follow-up

8.8.4.1 Adverse event reporting

The investigator or designee (as per site delegation log) is responsible for obtaining, assessing, and documenting all AEs during the trial.

Adverse event information will be collected from individual trial patients from signature of the informed consent form until the last trial visit.

All AEs will be documented in the eCRF, including a description of each AE, AE relationship to IMP, start and stop dates, seriousness, severity, action taken (with the IMP and other actions taken) and outcome.

If the event is reported as an SAE, the timelines for SAE reporting apply (see Section [8.8.4.2](#)). If the event is reported as non-serious AE, it should be reported on the appropriate eCRF page.

Throughout the trial, the occurrence of AEs should be monitored by nondirective questioning of the patient at each visit. Information on AEs can also be obtained from signs and symptoms detected during examinations, observations made by the site staff, or spontaneous reports from patients. Pre-existing conditions that worsen during the trial should also be recorded as AEs. This will also include worsening of the disease as judged by the investigator.

AEs requiring therapy must be treated in accordance with recognised standards of medical care to protect the health and well-being of the patient. Treatment due to an AE will be recorded in the patient's records and on the appropriate eCRF.

All SAEs and related non-serious AEs must be followed by the investigator until they are resolved or until judged by the investigator to be stable/need no further follow-up. Unrelated non-serious AEs must be followed by the investigator until the patient's last trial visit. All relevant follow-up information will be reported in the eCRF (and to PharmaLex if it qualifies as an SAE, see Section 8.8.9.1).

8.8.4.2 Serious adverse event reporting

Any SAE, whether by the investigator considered IMP-related or expected or not, must be reported immediately to PharmaLex as soon as it becomes known to the investigator and not later than within 24 hours of his/her knowledge of the occurrence of an SAE (see Section 8.8.9.1). For each SAE, the investigator will complete a Serious Adverse Event Report Form and assess the relationship of each SAE to trial treatment.

Follow-up report forms regarding the status of the SAE and the participant's subsequent course should be submitted to PharmaLex immediately and not later than 24 hours of follow up information awareness and until the SAE has resolved, is stabilised or needing no further follow-up (in the case of persistent impairment) or the patient dies.

The forms and acknowledgment of receipt will be retained by both the site and PharmaLex. For contact details for reporting SAEs, pregnancies and other safety concerns, refer to Section 8.8.9.1. The investigator will document such events in the best possible detail on the SAE Report Form.

A suspected unexpected serious adverse reaction (SUSAR) is an SAE that is both unexpected (not listed in the Reference Safety Information (RSI) Section 6.2.12 of the IB, and for which there is evidence to suggest a causal relationship between the IMP and the SAE. The National Competent Authorities (NCA), Institutional Review Board (IRB)/Independent Ethics Committee (IEC) will be informed of SUSARs and other safety issues according to local requirements, via Eudravigilance. All investigators participating in the trial will also be notified of SUSARs and other safety issues as applicable.

Investigator instructions for reporting SAEs and contact information are provided in Section 8.8.9.1. SAEs occurring after a patient has completed the trial and deemed IMP-related by the investigator should be reported to the sponsor within 24 hours from the investigator's awareness.

8.8.5 Reporting events to participants

Not applicable

8.8.6 Events of special interest

Not Applicable

8.8.7 Reporting of pregnancy

Any pregnancy occurring from the date of the informed consent signature until trial completion must be recorded in the eCRF and reported to PharmaLex as soon as possible, but no later than 24 hours from the investigator's awareness of the pregnancy (see Section 8.8.9.1).

The investigator must actively follow-up, document, and report to PharmaLex the progress of the pregnancy until outcome is reached.

8.8.8 Trial medication overdose and trial medication errors

An overdose of the IMP is a dose that is higher than the highest dose under clinical investigation.

In the event of a clinically significant overdose, as judged by the investigator, the event should be reported as an AE and supportive treatment or discontinuation of the IMP may be instigated as judged by the investigator. In view of the high systemic safety margin (see Section 4.2), the administered dose may be several folds higher than the highest dose under clinical investigation without necessarily qualifying as a clinically significant overdose.

A trial medication error is when the trial medication is used outside the dosing regimen specified in the protocol. In the event of a clinically significant trial medication error, as judged by the investigator, the event should be reported as an AE and supportive treatment or discontinuation of the IMP may be instigated as judged by the investigator.

9.1 Statistical hypotheses

On the primary and all secondary endpoints, treatment groups will be compared for superiority of MC2-25 cream over MC2-25 vehicle. The null hypothesis is of no difference between the two treatment groups. For further details see Section 9.4.1.

9.2 Sample size determination

Sixty two (62) patients will be screened. 33 patients will be randomised in a 1:1 ratio of MC2-25 cream to MC2-25 vehicle. For a two-sided test with a 5% level of significance and an effect size of 1 standard deviation, this sample size will provide adequate power ($\geq 78\%$) to compare mean change in mean weekly WI-NRS from Baseline to Week 12 between MC2-25 cream and MC2-25 vehicle with 16 to 17 patients per treatment group.

9.3 Populations for analyses

The analysis populations are defined as follows:

Screened set (SS): all patients who sign the informed consent form.

Safety analysis set (SAS): all patients who are randomised and dispensed the trial medication at Randomisation/Day 0, excluding patients to whom trial medication is not dispensed or who return all the trial medication unused. Patients will be analysed according to the actual treatment.

Full analysis set (FAS): all patients who are randomised. Patients will be analysed according to the randomised treatment.

Modified full analysis set (MFAS): all patients who are randomised and returned for at least one post-baseline scheduled visit with data on weekly mean WI-NRS. Patients will be analysed according to the randomised treatment.

Per-protocol set (PPS): a subset of the MFAS patients who completed the trial with WI-NRS data for Week 12 and are deemed to have no important protocol deviations that could interfere with the objectives of this trial. Important deviations of eligibility criteria and other deviations from the protocol will be assessed. Important deviations from the protocol may lead to exclusion of a patient or data points from the PPS, which could have interfered with the administration of the treatment or the evaluation of treatment effect. All such decisions will be identified and documented before the final trial database is unblinded. Important protocol deviations may include, but are not limited to, medication non-compliance, missing consecutive application days, and intake of prohibited concomitant therapies, which may have an impact on the primary endpoint.

The SAS will be used for all safety analyses. FAS, MFAS, and PPS will be used for efficacy analyses.

9.4 Statistical analyses

9.4.1 General approach

The methodology presented below represents a brief overview of the statistical methods that will be fully detailed in the statistical analysis plan (SAP). The SAP will be finalised before the database is locked. Any changes to the methods described in the final SAP will be described and justified in the clinical trial report. All statistical analyses will be performed using SAS statistical software (Version 9.4 or higher).

Statistical significance will be tested at the two-sided 5% significance level unless otherwise specified. Superiority is concluded if a p-value of statistical hypothesis testing is below the significance level and the estimate of treatment difference is in favourable direction for MC2-25 cream. Estimates of treatment effects and differences at timepoints other than Week 12 will be reported exploratively.

Categorical variables will be described by summary tables of frequencies (counts and percentages) per treatment group, continuous parameters by displaying arithmetic mean, median, minimum and maximum values, standard deviation, and, where applicable, interquartile ranges.

All collected and derived data will be presented in individual patient data listings.

9.4.2 Analysis of efficacy

On the FAS, all efficacy endpoints will be analysed, the primary endpoint also on the MFAS and the PPS. All endpoints, including PROs and HRQoL questionnaires, will be summarised as observed. For statistical analyses of primary and secondary endpoints, missing values will be imputed by different approaches described below. Further details will be given in the SAP.

9.4.2.1 Analysis of the primary efficacy endpoint

The primary endpoint, mean change in weekly mean WI-NRS from baseline to Week 12 for MC2-25 cream compared to MC2-25 vehicle, will be analysed by a mixed model of repeated measures (MMRM) including all post-baseline assessments. The model will include the fixed effects of treatment, visit, treatment-by-visit interaction, menopausal status at baseline, ICIQ-UI-SF score at baseline, and weekly mean WI-NRS at baseline. The mean change in WI-NRS at Week 12, as well as the treatment difference will be estimated using LS-means and reported together with the associated standard error, 95% confidence intervals and p-values based on F-statistics.

On the FAS, for the primary analysis assuming missingness at random, missing data will be imputed 20 times and summarised following Rubin's rule. Following a treatment policy approach, all data will be considered.

Applying the same statistical model, in sensitivity analyses MMRM will be applied to observed cases on the FAS, MFAS and PPS, respectively, without imputation. In a while-on-treatment approach, in another sensitivity analysis on the FAS, only data up to the week of treatment

discontinuation will be considered. As detailed in the SAP, further sensitivity analyses may consider assumption of missingness not at random and other potential intercurrent events.

9.4.2.2 Analysis of the secondary endpoints

Secondary endpoints include mean changes in weekly mean WP-NRS and in Skindex-29 domain scores as well as percentages of participants obtaining a ≥ 3 -point or a ≥ 4 -point improvement in weekly mean WI-NRS and weekly mean WP-NRS, respectively.

Mean changes in weekly mean WP-NRS and in Skindex-29 domain scores on the FAS will be analysed as described in Section 9.4.2.1 for primary and sensitivity analyses on mean changes in weekly mean WI-NRS. On the FAS, percentages of participants obtaining a ≥ 3 -point or a ≥ 4 -point improvement in weekly mean WI-NRS and weekly mean WP-NRS will be analysed by means of logistic regression adjusting for respective NRS scores at baseline. If the endpoint is missing, no improvement is assumed.

9.4.3 Safety analyses

9.4.3.1 Safety analyses – General

On the SAS, safety will be analysed by means of incidences of AEs, changes in vital signs and physical examination.

9.4.3.2 Adverse events

Adverse events will be coded using Medical Dictionary for Regulatory Activities (MedDRA) terminology. Treatment-emergent adverse events (TEAEs), related TEAEs, non-serious TEAEs, serious TEAEs, related serious TEAEs, TEAEs leading to treatment discontinuation and deaths will be summarised by the overall incidence of at least one event, incidence by body system, and incidence by body system and preferred term. Each patient will contribute only once (e.g., the first occurrence) to each of the rates, regardless of the number of occurrences (events) the patient experiences. The number of occurrences will also be displayed.

Treatment-emergent AEs will be summarised by severity (mild, moderate, or severe), and by relationship to trial product (not related, unlikely, possibly, or probably). In summaries of severity and relationship, patients who report more than one event that are mapped to the same preferred term will be counted only once under the strongest severity and last relationship, accordingly. An AE is treatment-emergent if its date of onset is on or after the day of start of trial medication. An AE is related if relationship to trial product is not assessed as unrelated.

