### 5.5.4 Safety Endpoints

Safety endpoints will be described by summary tables on the Safety Analysis Set (SAS).

Treatment-emergent AEs, treatment-emergent drug-related AEs, treatment-emergent serious AEs (SAE), treatment-emergent drug-related SAEs, treatment-emergent AEs leading to drug withdrawal and treatment-emergent drug-related SAEs leading to drug withdrawal will be presented in summary tables of the number and percentage of patients with at least one event, and the number of events, by primary SOC and by PT within SOC. For treatment-emergent AEs and treatment-emergent drug-related AEs, these summaries will also be provided by maximum severity. Maximum severity is defined by the most severe AE per patient, SOC and PT. An overview will summarize incidences in all listed AE categories including deaths.

Vital signs will be summarized by visit including changes from baseline, as well as a shift table with categories: normal, abnormal/non-clinically significant, and abnormal/clinically significant. For physical examination, frequency counts of the complete examination (including all body systems and the vulvar region) at Screening 1 and Week 12 (or EoT) visits as well as the results of the abbreviated physical examination at the baseline and FU visits (if judged necessary by the investigator), will be reported in both

a table with percentages as well as a shift table with categories: normal, abnormal/non-clinically significant, and abnormal/clinically significant. Frequency counts and percentage of urine pregnancy tests will also be presented.

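### Protocol 9.4.3.2 applies a within-event rule (last relationship) across separate adverse events, so the promised by-relationship summary can lose a patient's strongest relationship grade (minor)

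*Protocol*

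**What the plan says.** Protocol 9.4.3.2 sets two counting rules.

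- **Incidence.** Several classes of treatment-emergent adverse event (TEAE), among them related TEAEs and related serious TEAEs, "will be summarised by the overall incidence of at least one event, incidence by body system, and incidence by body system and preferred term". The number of occurrences is shown as well. An event counts as related unless it was assessed as unrelated.
- **Breakdown.** TEAEs are also summarised by severity and "by relationship to trial product (not related, unlikely, possibly, or probably"). A different rule applies, limited to these two summaries. It says that patients with "more than one event that are mapped to the same preferred term will be counted only once under the strongest severity and last relationship".

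Protocol 8.8.3 has its own rules for a single event. Under 8.8.3.1 the maximum severity is final. Under 8.8.3.2, "The last relationship recorded during the course of an AE will be considered the final relationship", on the ground that the investigator then knows most.

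In SAP 5.5.4 the TEAE classes, including drug-related TEAEs and drug-related serious TEAEs, "will be presented in summary tables of the number and percentage of patients with at least one event", with the number of events. A further breakdown is given by maximum severity only. The table list in SAP 7.3 has Table 14.3.1.4 (drug-related TEAEs) and Table 14.3.1.7 (drug-related serious TEAEs), but no table by relationship category. SAP 5.6, which records changes from the protocol, does not mention this.

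**The concern.** Protocol 9.4.3.2 appears to carry both single-event rules of 8.8.3 over to several events in one patient. For severity this is harmless, since the maximum of several maxima is still the maximum. For relationship it is not. The last assessment of one event is the best-informed view of that event. The last of several separate events is only the most recent, and its grade says nothing about what caused the others. The sentence therefore keeps a woman's worst severity but can drop her strongest attribution.

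The four-category breakdown is the only aggregate summary in either document that separates *unlikely*, *possibly* and *probably*; the related-event counts merge all three. A lost *probably* would then be visible only in the individual listing (SAP Listing 16.2.7.1.1). Safety against vehicle is a secondary objective, application site reaction is the first risk named in Protocol Table 2, and the cream is applied after each toilet visit. Local symptoms recurring under one preferred term are therefore a realistic case.

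**Working it through.** The documents give no adverse event rates and no figure on this point, so the check is textual, followed by an illustration on stated assumptions.

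**Step 1. Apply each rule to one woman with two treatment-emergent events of the same preferred term.**

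| Event 1, then event 2 | Breakdown as written (last) | Breakdown with strongest grade | Related incidence (at least one) |
|---|---|---|---|
| probably, then not related | not related | probably | counted |
| probably, then unlikely | unlikely | probably | counted |
| not related, then probably | probably | probably | counted |
| not related, then not related | not related | not related | not counted |

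Row 1 is an internal contradiction in 9.4.3.2: the same woman is related in one summary and not related in the other. Row 2 is no contradiction, but her strongest grade disappears from every aggregate. Row 3 shows that the last event can also carry the higher grade. The last column is the same whichever rule the breakdown uses.

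**Step 2. Direction.** If the last event is related, at least one event is related; the converse does not hold. So the number of women shown in the three related categories under the last-event rule is equal to or below the at-least-one count, never above it. Under the strongest-grade rule the two counts agree for each preferred term.

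**Step 3. Size within the breakdown (assumed inputs).** Suppose a woman has k events of one term, each related with probability p, independently. The last-event rule shows her as related with probability p; the at-least-one rule counts her with probability 1 − (1 − p)^k. Among women with at least one related event of that term, the share shown as *not related* is 1 − p / [1 − (1 − p)^k].

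| p | k = 2 | k = 3 |
|---|---|---|
| 0.1 | 1 − 0.1/0.190 = 47% | 1 − 0.1/0.271 = 63% |
| 0.3 | 1 − 0.3/0.510 = 41% | 1 − 0.3/0.657 = 54% |
| 0.5 | 1 − 0.5/0.750 = 33% | 1 − 0.5/0.875 = 43% |
| 0.7 | 1 − 0.7/0.910 = 23% | 1 − 0.7/0.973 = 28% |

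**Step 4. The same in counts.** Protocol 9.2 gives 16 to 17 patients per arm. Take 17, with Clopper-Pearson 95% limits.

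- One woman with a *probably* and then a *not related* event: 1/17 = 5.9% (0.1 to 28.7%) becomes 0/17 (upper limit 19.5%).
- Four women with at least one related event and a repeat, the last event *not related* in two: 4/17 = 23.5% (6.8 to 49.9%) becomes 2/17 = 11.8% (1.5 to 36.4%).

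These shifts occur only in the four-category breakdown. In the related-TEAE incidence and in SAP Tables 14.3.1.4 and 14.3.1.7 the counts stay at 1 and 4.

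**The case against.** A reader might infer that related reactions are undercounted in this trial. The documents do not support that. Protocol 9.4.3.2 itself counts related TEAEs by at least one related event and shows the number of occurrences, and it limits the last-relationship rule to the severity and relationship summaries. A reader might also infer that protocol and SAP count drug-related events differently. They do not: SAP 2.4.2 and 5.5.4 use the same per-event definition and the same at-least-one count, so SAP 5.6 had no changed counting rule to declare.

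It can further be said that no listed SAP table uses the rule, that Protocol 9.4.1 calls its methods an overview which the SAP will detail, and that every event is listed individually. All of this is true, and it makes the point minor. It does not remove it. SAP section 1 says that analysis follows the protocol, and the protocol promises the breakdown. If the breakdown is produced, it follows the faulty rule; if not, a promised summary has been dropped without being declared.

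One could read the last relationship as the final within-event assessment of 8.8.3.2. But the sentence concerns patients with several events, each counted once, so a choice between events is needed and this is the only one it gives.

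It is tempting to add that recurrences in the two-week follow-up would usually be judged unrelated. The protocol sets no end date for a TEAE ("An AE is treatment-emergent if its date of onset is on or after the day of start of trial medication"), so such a recurrence would count and would come last. How it would be graded is not stated anywhere, and nothing here relies on it.

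**Conclusion.** The point holds in a limited form and is minor. Protocol 9.4.3.2 extends to separate events a rule that 8.8.3.2 justifies only within one event. In the by-relationship summary alone, a patient's strongest grade can be lost, and a *not related* last event contradicts the related-TEAE incidence in the same section. The related-event rates planned in both documents are unaffected. The counts and percentages above rest on assumed event patterns, with independent events in the table of shares, and show only how far the breakdown could move in arms of this size. Separately, the SAP omits the by-relationship summary without saying so in 5.6.

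**What to change.** In Protocol 9.4.3.2, replace the relationship half of the rule. Suggested wording: *A patient with several treatment-emergent events under one preferred term appears once, at her highest severity and at her highest relationship grade (order: probably, possibly, unlikely, not related).* Keep the last relationship only for repeated assessments of one event, as in 8.8.3.2.

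In the SAP, do one of two things: add a by-relationship table to the list in 7.3 and state this rule in 5.5.4, or declare in 5.6 that the summary promised in the protocol is not produced.

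The cost is one phrase in the protocol and either one sentence or one table with its rule in the SAP. No new data are needed. The by-relationship summary may look slightly less favourable; the related-event incidence does not change.
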